### 6.1.1.4 Subgroup Analysis

Subgroup analyses will be performed to examine the consistency of results for the primary safety endpoint. Analysis will be based on Fisher's exact test. No subgroup specific labeling claims are desired for this endpoint and no adjustments for multiplicity will be made. Subgroups to be examined include, but are not limited to, those defined by achieving >90% of lesions with  $\geq 10$ g contact force, age (both <65 vs  $\geq 65$  and age  $\geq$  median vs < median), sex, and race/ethnicity.

## 6.1.2 Primary Effectiveness Endpoint Hypothesis

The performance goal is set at 90% based on experience from previous IDE trials of approved devices relying on pulmonary vein isolation for effectiveness. The hypothesis is formally expressed as:

$$H_0: P < 90\%$$
$$H_A: P \geq 90\%$$

where P is the percentage of subjects with acute success. The hypothesis will be tested based on a one-sided exact test of binomial proportions at the one-sided 0.05 alpha level. Rejection of the null hypothesis will indicate study success.

### 6.1.2.1 Analysis Methodology

The primary effectiveness endpoint event rate will be calculated based on the number of subjects experiencing a primary effectiveness endpoint divided by the total number of subjects in the analysis population. The null hypothesis will be rejected if the lower bound of the one-sided 95% confidence interval for the proportion of subjects in this trial with the primary effectiveness endpoint is greater than 90%.

[REDACTED]

### 6.1.2.3 Analysis Population

The analysis population for this endpoint will include enrolled subjects who have also had the TactiCath SE inserted into their vasculature.

### 6.1.2.4 Subgroup Analysis

Subgroup analyses will be performed to examine the consistency of results for the primary effectiveness endpoint. Analysis will be based on Fisher's exact test. No subgroup specific labeling claims are desired for this endpoint and no adjustments for multiplicity will be made. Subgroups to be

[REDACTED]

examined include, but are not limited to, those defined by age (both <65 vs ≥65 and age ≥ median vs < median), sex, and race/ethnicity.

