### **5.1.7 Subgroup Analysis**

Subgroup analyses will be performed to examine the consistency of the primary safety endpoint event rate across subgroups. Subgroups to be examined include, but are not limited to, those defined by achieving >90% of lesions with  $\geq 10$ g contact force, age (both <65 vs  $\geq 65$  and age  $\geq$  median vs < median), sex, and race/ethnicity. Since the number of subjects not achieving >90% lesions with  $\geq 10$ g contact force in this study is likely to be small, the results from similar subjects from the Toccstar IDE study will be pooled with results from this trial. The results for this endpoint will be presented separately for those achieving/not achieving >90% of lesions with  $\geq 10$ g contact force. As needed and appropriate (i.e., for comparison of subgroups), categorical variables will be tested using Fisher's exact test and continuous variables will be tested using two sample t-test. No subgroup specific labeling claims are desired for the primary safety endpoint and no adjustments for multiplicity will be made.

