### **5.2.4 Subgroup Analysis**

Subgroup analyses will be performed to examine the consistency of results for the primary effectiveness endpoint. Analysis will be based on Fisher's exact test. No subgroup specific labeling claims are desired for this endpoint and no adjustments for multiplicity will be made. Subgroups to be examined include, but are not limited to, those defined by age (both <65 vs  $\geq 65$  and age  $\geq$  median vs < median), sex, and race/ethnicity.

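### Age consistency of both primary endpoints is pre-specified as two overlapping splits tested by Fisher's exact test, with no analysis of age in years and no interval for any subgroup difference

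*Protocol*

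**What the plan says.** Protocol 6.1.1.4 and SAP 5.1.7 (safety) and Protocol 6.1.2.4 and SAP 5.2.4 (effectiveness) give the same two age splits. The purpose is consistency: "Subgroup analyses will be performed to examine the consistency of results for the primary safety endpoint" in the Protocol, and "Subgroup analyses will be performed to examine the consistency of results for the primary effectiveness endpoint" for effectiveness in the SAP. For effectiveness the named subgroups are "those defined by age (both <65 vs ≥65 and age ≥ median vs < median), sex, and race/ethnicity", and all four sections state that their list is open-ended.

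The test is Fisher's in both Protocol sections and in SAP 5.2.4: "Analysis will be based on Fisher's exact test". SAP 5.1.7 alone adds that, as needed for comparing subgroups, "categorical variables will be tested using Fisher's exact test and continuous variables will be tested using two sample t-test".

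On status: "No subgroup specific labeling claims are desired for this endpoint and no adjustments for multiplicity will be made". No subgroup significance level, effect size or power is given. The readable text plans no difference, ratio or interval between subgroups for either primary endpoint.

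**The concern.** A sample median can be formed only from numeric age, so age in years will be in the database. Cutting it in two discards the ordering within each half, and Fisher's test falls below its nominal level when events are few. The median split depends on the data and may largely repeat the split at 65.

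Without an interval, the reader judges consistency from a p-value. With few events, that p-value will usually be non-significant even when the data are compatible with a large difference between younger and older subjects.

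**Working it through.** The plan gives no subgroup power to reproduce, and its sample-size sections are redacted. Three checks follow.

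**1. How many events can a passing trial have?**

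Inputs: N = 140 (Protocol 6.5, SAP 5.6), goals of 16.2% and 90%, and one-sided 95% exact bounds.
- Safety: 15/140 has an upper bound of 16.0% and passes; 16/140 has 16.8% and fails.
- Effectiveness: 7 failures (133/140) have a lower bound of 90.8% and pass; 8 failures give 89.9% and fail.

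A successful trial of this size therefore has at most 15 safety events and 7 acute failures.

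**2. What does Fisher's test say about that few events?**

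Take two halves of 70. If all f failures fall in one half, the two-sided p-value is 2·C(70,f)/C(140,f).
- f = 5: p = 0.058.
- f = 6: p = 0.028.

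Safety examples, with 95% hybrid score intervals for the difference:
- 3/70 v 8/70: p = 0.21; difference 7.1 points, interval -2.2 to 17.1.
- 4/70 v 11/70 (15 events, still a pass): p = 0.10; difference 10.0 points, interval -0.5 to 20.8.

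Both safety comparisons are non-significant, yet their upper limits are near 17 and 21 points.

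**3. How much does splitting age cost?**

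Assumptions, none from the documents: age normal with mean 62 and SD 10; risk linear in age on the logit scale; two-sided 0.05; event rates and odds ratios (OR) per 10 years as shown. Simulation used 4,000 trials per setting, N = 140. The continuous test is the likelihood-ratio test in ordinary logistic regression. Ratio = power of either cut / power of continuous age, from unrounded powers.

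| Event rate | OR | Cut at 65 | Median cut | Either cut | Continuous age | Ratio |
|---|---|---|---|---|---|---|
| 5% | 1.5 | 9.9% | 5.2% | 11.7% | 18.9% | 0.62 |
| 5% | 2.0 | 23.9% | 12.1% | 26.7% | 42.2% | 0.63 |
| 8% | 1.5 | 14.1% | 9.5% | 17.6% | 25.3% | 0.69 |
| 8% | 2.0 | 35.3% | 25.6% | 41.0% | 58.1% | 0.70 |
| 10% | 1.5 | 16.1% | 13.0% | 20.8% | 29.4% | 0.71 |
| 10% | 2.0 | 43.6% | 35.3% | 49.5% | 66.0% | 0.75 |
| 12% | 1.5 | 18.9% | 15.6% | 23.9% | 33.2% | 0.72 |
| 12% | 2.0 | 48.9% | 41.0% | 56.1% | 72.4% | 0.77 |

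A repeat with the Firth-penalised test (3,000 trials per setting) gives ratios of 0.64 to 0.80, so the choice of logistic test changes little.

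- **Size of the tests.** With no age effect, at event rates of 5 to 12%, a single Fisher cut rejects in 1.6 to 3.6% of trials and ordinary logistic regression in 5.2 to 5.9%. Part of the loss therefore comes from Fisher's conservatism and not from the cut.
- **Overlap of the cuts.** Under the assumed age distribution, the share of subjects who change group between the cuts is Φ(0.3) - Φ(0) = 11.8%.
- **Mean age.** At an 8% rate and OR 2.0, the ratio is about 0.81, 0.70 and 0.57 for mean ages of 58, 62 and 65.
- **Shape.** For a true step at 65 (5% v 14%), the cut at 65 has 39% power and Firth regression on age 30%.
- **Effectiveness.** At 2 to 3% failures and OR 2.0, either cut has 8 to 16% power and continuous age 21 to 29%. At OR 1.5 and 2 to 5% failures, continuous age has only 10 to 18%.

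**The case against.** The strongest reply is that these are exploratory checks. They carry no labelling claim and play no part in the success criteria (Protocol 6.6, SAP 5.7), and the open-ended list already permits an age model. That stands and keeps the point minor. But permitting an analysis does not pre-specify it, and the t-test sentence in SAP 5.1.7 does not fill the gap: it covers safety only, does not name age, and is not a model of event risk.

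It is also fair that sparse events are the main limit. At an 8% rate and OR 1.5, continuous age still misses about three trends in four (power 25.3%). This stands too, and for effectiveness it means the gain lies mainly in the interval.

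Three stronger readings are tempting and are not supported:
- **That the plan halves the chance of seeing an age trend.** That roughly describes the median cut alone (25.6% v 58.1% at 8% and OR 2.0). The plan uses both cuts.
- **That an acute failure rate near 5% is what to expect.** The documents give no expected rate, and 5% is 7/140, the edge of passing.
- **That the generalisation to Medicare beneficiaries rests on these tests.** Protocol 4.4.3 bases it on expected overlap in demographics and cardiovascular risk factors. Nor do the documents say that a non-significant p-value establishes consistency.

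**Conclusion.** The concern holds as a minor improvement. For a smooth age trend, the two planned cuts together have about 62 to 77% of the power of a continuous-age model at an assumed mean age of 62. At an 8% rate and OR 2.0, varying the mean age from 58 to 65 moves this from about 81% to 57%. These figures rest on the assumed age distribution, event rates, slope, logit linearity and 0.05 level; a step at 65 would reverse the ranking.

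The missing interval matters more and needs none of the age or slope assumptions. With at most 15 safety events and 7 acute failures in a passing trial of 140, a non-significant Fisher test says little about consistency. The primary tests and the success criteria are untouched.

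**What to change.** In SAP 5.1.7 and 5.2.4, with Protocol 6.1.1.4 and 6.1.2.4 amended to match:

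1. Keep the table of under 65 against 65 and over. The median split may stay for presentation.
2. For primary safety, add a Firth-penalised logistic regression on age in years, reporting the odds ratio per 10 years with a 95% confidence interval.
3. For both primary endpoints, report each between-subgroup difference in rates with an exact or score 95% interval beside the Fisher p-value. Name the interval method in advance, because an interval and Fisher's test can disagree near the boundary.
4. State that non-significance alone will not be taken as evidence of consistency.
5. For effectiveness, a continuous-age odds ratio may be added as descriptive only, because failures will be very sparse.

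The cost is a few lines of text and one standard model, using data already collected. The downside is the assumption that log-odds change linearly with age, which keeping the cut at 65 covers. The analyses stay exploratory.

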### 6.1.3 Descriptive Endpoint #1

Descriptive endpoint #1 is ablation data collected during the procedure, including:

- Power
- Temperature
- Irrigation flow rate
- Contact force
- Procedure time
- Total ablation time
- Total fluoroscopy time
- Total RF application time
- Usage of Automark

#### 6.1.3.1 Analysis Methodology

Descriptive statistics will be generated for all variables.

#### 6.1.3.2 Analysis Population

The analysis population for this endpoint will include all enrolled subjects who have also had the TactiCath SE inserted into their vasculature and radiofrequency energy was delivered.

### 6.1.4 Descriptive Endpoint #2

Descriptive endpoint #2 is the proportion of index cases achieving ≥ 90% lesions with ≥10g contact force.

#### 6.1.4.1 Analysis Methodology

Subjects with at least 90% of lesions with ≥10g achieved will be divided by the analysis population. Corresponding exact two-sided 95% binomial confidence intervals will also be calculated.

#### 6.1.4.2 Analysis Population

The analysis population for this endpoint will include all enrolled subjects who have also had the TactiCath SE inserted into their vasculature and radiofrequency energy was delivered.

### 6.1.5 Descriptive Endpoint #3

Descriptive endpoint 3 is defined as serious adverse events and adverse events related the device and/or ablation catheter through 30 days post ablation.

#### 6.1.5.1 Analysis Methodology

The number and percentage of subjects experiencing adverse events will be summarized, by seriousness and relatedness. Corresponding exact two-sided 95% binomial confidence intervals will also be calculated. Subjects who terminate the study prematurely without experiencing any adverse events through 30 days post ablation will not be considered as having any events for this analysis.

#### 6.1.5.2 Analysis Population

The analysis population for this endpoint will include all enrolled subjects who have also had the TactiCath SE inserted into their vasculature.

#### 6.1.6 Descriptive Endpoint #4

Descriptive endpoint 4 is defined as serious adverse events and adverse events related the device and/or ablation catheter through 1 year post ablation.

##### 6.1.6.1 Analysis Methodology

The number and percentage of subjects experiencing adverse events will be summarized, by seriousness and relatedness. Corresponding exact two-sided 95% binomial confidence intervals will also be calculated. Subjects who terminate the study prematurely without experiencing any adverse events through 1 year post ablation will not be considered as having any events for this analysis.

##### 6.1.6.2 Analysis Population

The analysis population for this endpoint will include all enrolled subjects who have also had the TactiCath SE inserted into their vasculature.

#### 6.1.7 Descriptive Endpoint #5

Descriptive endpoint #5 is one-year success, defined as freedom from symptomatic AF/AFL/AT lasting at least 30 seconds without a new Class I or III AAD or a higher dosage of pre-existing AAD as assessed from the end of the 3-month blanking period to 12 months following the ablation procedure.

A full 10-second 12-lead ECG recording of arrhythmia may be substituted for a 30-second recording unless there is evidence that the recorded arrhythmia is short-lived and less than 30 seconds.

##### 6.1.7.1 Analysis Methodology

Freedom from AF will be calculated as the number of subjects without a failure as defined in section 6.1.7 divided by the total number of subjects in the analysis population. Corresponding exact two-sided 95% binomial confidence intervals will also be calculated.

##### 6.1.7.2 Analysis Population

The analysis population for this endpoint will include all enrolled subjects who have also had the TactiCath SE inserted into their vasculature and who have completed their 1-year visit or crossed the 1-year visit window without the visit but with an event as defined above for the descriptive endpoint #5. In addition, the analysis will be run on the subset of subjects who also meet descriptive endpoint #2 (achieving  $\geq 10$ g contact force).

#### 6.1.8 Descriptive Endpoint #6

Descriptive endpoint #6 is one-year drug-free success, defined as freedom from any AF/AFL/AT lasting at least 30 seconds or any Class I or III AAD after removal from antiarrhythmic drug therapy as assessed from the end of the 3-month blanking period to 12 months following the ablation procedure.

A full 10-second 12-lead ECG recording of arrhythmia may be substituted for a 30-second recording unless there is evidence that the recorded arrhythmia is short-lived and less than 30 seconds.

##### 6.1.8.1 Analysis Methodology

Freedom from AF will be calculated as the number of subjects without a failure as defined in section 6.1.8 divided by the total number of subjects in the analysis population. Corresponding exact two-sided 95% binomial confidence intervals will also be calculated.

##### 6.1.8.2 Analysis Population

The analysis population for this study will be based on all subjects in whom a study device was introduced and who have completed their 1-year visit or crossed the 1-year visit window without the

visit but with an event as defined above for the descriptive endpoint #6. In addition, this analysis will be performed on the following subsets of subjects:

- Subjects who are also off of antiarrhythmic medication at the end of the blanking period.
- Subjects who also meet descriptive endpoint #2 (achieving  $\geq 10g$  contact force).

#### 6.1.9 Descriptive Endpoint #7

Descriptive endpoint #7 is change in EQ-5D-5L scores from baseline to follow up at 3, 6, and 12 months.

##### 6.1.9.1 Analysis Methodology

Changes in EQ-5D-5L score between baseline and follow up visits will be summarized with descriptive statistics. Scores will be used to calculate utility values and QALYs.

##### 6.1.9.2 Analysis Population

The analysis population for this endpoint will include all enrolled subjects who have also had the TactiCath SE inserted into their vasculature, have a baseline EQ-5D-5L, and who have completed their applicable follow up visit.

#### 6.1.10 Descriptive Endpoint #8

Descriptive endpoint #8 is change in AFEQT scores from baseline to follow up at 3, 6, and 12 months.

##### 6.1.10.1 Analysis Methodology

Changes in AFEQT between baseline and follow up visits will be summarized with descriptive statistics to assess change in functional improvement.

##### 6.1.10.2 Analysis Population

The analysis population for this endpoint will include all enrolled subjects who have also had the TactiCath SE inserted into their vasculature, have a baseline AFEQT, and who have completed their applicable follow up visit.

#### 6.1.11 Descriptive Endpoint #9

Descriptive endpoint #9 is cardiovascular-related health care utilization through 12 months post index ablation.

##### 6.1.11.1 Analysis Methodology

Descriptive statistics will be generated for all variables.

##### 6.1.11.2 Analysis Population

The analysis population for this endpoint will include all enrolled subjects who have also had the TactiCath SE inserted into their vasculature and who have health care utilization data available.

#### 6.1.12 Descriptive Endpoint #10

Descriptive endpoint #10 is force time integral (FTI) and lesion index (LSI).

##### 6.1.12.1 Analysis Methodology

FTI and LSI will be derived from the available Ensite Precision data. Descriptive statistics will be generated for both variables.

### 6.1.12.2 Analysis Population

The analysis population for this endpoint will include all enrolled subjects who have also had the TactiCath SE inserted into their vasculature.

[REDACTED]

[REDACTED]

### 6.3 Multiplicity

Both primary endpoints must pass hypothesis testing for the trial to be a success. Descriptive endpoints and subgroup analyses are not intended to support labeling claims. Therefore, multiplicity adjustment is not applicable.

[REDACTED]

[REDACTED]

### 6.5 Timing of Analysis

The primary endpoint analysis will be performed and the pre-market approval (PMA) clinical report will be submitted when 140 subjects have data available to assess the primary safety and effectiveness endpoints.

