## 4 Clinical Investigation Design

### 4.1 Clinical Investigation Design

This is a prospective, multi-center, single-arm clinical trial to demonstrate the acute safety and effectiveness of the TactiCath SE catheter for the treatment of PAF against a performance goal. One hundred fifty six (156) subjects will be enrolled at up to 35 investigational sites in the US, Europe, and Australia. Only sites that enroll at least one subject will be part of the analysis population. No center may contribute more than 20% of the total number of enrollments without sponsor pre-approval to exceed this proportion and at least 50% of subjects must be from the United States.

[REDACTED] Subjects will be followed for 12 months after the index ablation procedure and then exit the clinical trial. [REDACTED]

[REDACTED] The pre-market approval (PMA) clinical report will be submitted when at least 140 subjects have been enrolled, had the investigational catheter inserted into their vasculature, and either experienced an event as defined in section 4.3.1, completed their 30 day follow up visit, or have been lost to follow up per section 5.7.

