### 5.7 Subject Withdrawal

Subjects must be informed about their right to withdraw from the clinical investigation at any time and for any reason without sanction, penalty or loss of benefits to which the subject is otherwise entitled. Withdrawal from the clinical investigation will not jeopardize their future medical care or relationship with the investigator. Subjects will be requested to specify the reason for the request to withdraw. The investigator must make all reasonable efforts to retain the subject in the clinical investigation until completion of the clinical investigation.

A subject will be considered 'Lost to Follow-up' after one missed visit(s) and a minimum of two unsuccessful phone calls from investigational site personnel to the subject or subject's contact to schedule the next follow-up visit. These two phone calls must be documented in the subject's hospital records. If the subject is deemed lost to follow-up, a letter should be sent to the subject's last known address or to the subject's general practitioner (GP) and a copy of the letter must be maintained in the subject's hospital records.

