### 6.1.1.3 Analysis Population

The analysis population for this endpoint will include all enrolled subjects who have also had the TactiCath SE inserted into their vasculature, and either had an event or completed a visit at or beyond their 30-day follow up visit window. Subjects without an event that are lost to follow up without a visit at or beyond their 30-day follow up visit window will be excluded from this analysis.

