## 3 TRIAL DESIGN

This is a prospective, multi-center, single-arm clinical trial to evaluate the acute safety of the TactiCath SE catheter for the treatment of paroxysmal atrial fibrillation (PAF) against a performance goal. One hundred fifty six-(156) subjects will be enrolled at up to 35 investigational sites in the US, Europe, and Australia. Only sites that enroll at least one subject will be part of the analysis population. No center may contribute more than 20% of the total number of enrollments without sponsor pre-approval to exceed this proportion and at least 50% of subjects must be from the United States.

In addition to PVI, subjects with documented atrial flutter, AT or other SVT (spontaneous or induced) may undergo additional targeted ablation as clinically indicated.

**[REDACTED]** Subjects will be followed for 12 months after the index ablation procedure and then exit the clinical trial. **[REDACTED]** The pre-market approval (PMA) clinical report will be submitted when at least 140 subjects have been enrolled, had the investigational catheter inserted into their vasculature and either experienced an event as defined in CIP section 4.3.1, completed their 30 day follow up visit, or have been lost to follow up per CIP section 5.7.

A CEC will be responsible for providing an independent review and adjudication of adverse events. The primary function, responsibilities and membership of the CEC will be described in detail in a CEC charter.

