### 5.1.4 Analysis Population

The analysis population for this endpoint will include all enrolled subjects who have also had the TactiCath SE inserted into their vasculature, and either had an event or completed a visit at or beyond their 30-day follow up visit window. Subjects without an event that are lost to follow up without a visit at or beyond their 30-day follow up visit window will be excluded from this analysis.

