#### 5.1.5.2 Multiple Center Effect

Analysis will be performed by pooling data across study sites. The TactiSense trial will have 35 sites globally, with at least 50% of subjects in the United States. Subject enrollment is capped at 28 per site (20% of the total number of enrollments). This cap per site will prevent the scenario where the results from a few sites dominate the overall study result. For the analysis of center effect, data from smaller sites may be combined for the analysis. Smaller sites are defined as sites with fewer than 12 subjects per site. The pooling of the smaller sites will be based on the following rules:

[REDACTED]

- Sort all smaller sites based on the number of subjects per site in an ascending order. If there are ties, sort further by site number.
- Starting from the smallest site in this list, combine sites by going up the list until the combined group size first reaches 12 or larger. At this point, a super site is identified.
- Repeat the above grouping process from the next smallest site above the newly formed super site.
- The grouping process ends when all smaller sites have been accounted for.

The sizes of the super sites (which are a result of grouping smaller sites) will range between 12 and up to 22 (11+11). This represents a reasonable range of sample sizes which will provide meaningful estimates of within-sites variations and will not alter between-sites variation.

To evaluate the multiple center effect on the primary safety endpoint, Fisher's exact test will be tested for center effect in the TactiSense trial against an alpha level of 0.15.

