### **5.1.6 Sensitivity Analysis**

To demonstrate robustness with respect to missing data, a tipping point analysis will be performed for the primary safety endpoint. This will involve imputing all possible combinations of outcomes for the primary endpoint among subjects who terminate the study prematurely without experiencing any primary safety endpoint events.

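### The two statements of the 140-subject trigger count different subjects, and no visible rule closes the safety cohort by insertion

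*Protocol*

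**What the plan says.** **Trigger for the PMA report (protocol 4.1, SAP 3).** At least 140 subjects must have had the catheter inserted and have "either experienced an event as defined in section 4.3.1, completed their 30 day follow up visit, or have been lost to follow up". The SAP has the same rule: "completed their 30 day follow up visit, or have been lost to follow up per CIP section 5.7".

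**Trigger for the primary analysis and the same report (protocol 6.5, SAP 5.6).** Both happen "when 140 subjects have data available to assess the primary safety and effectiveness endpoints".

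**Safety analysis population (protocol 6.1.1.3, SAP 5.1.4).** Treated subjects who "either had an event or completed a visit at or beyond their 30-day follow up visit window". The excluded group is "Subjects without an event that are lost to follow up without a visit at or beyond their 30-day follow up visit window".

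**Lost to follow-up (protocol 5.7).** The status applies "after one missed visit(s) and a minimum of two unsuccessful phone calls".

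**Missing data (SAP 5.1.6).** The tipping-point analysis imputes outcomes "among subjects who terminate the study prematurely without experiencing any primary safety endpoint events".

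**Effectiveness population (protocol 6.1.2.3, SAP 5.2.3).** All subjects with the catheter inserted, with no follow-up condition.

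Enrolment is 156, counted from consent (protocol 5.2). Subjects found ineligible before insertion leave the trial (protocol 5.3.1).

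**The concern.** Two things are left open for a co-primary test.

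First, an event-free subject who is lost counts toward 140 under protocol 4.1 but is not in the safety denominator. If the report were released on 4.1 alone, the safety test would run on fewer than 140.

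Second, entry to the safety set depends on outcome. Most qualifying events fall within 7 days of the procedure, and a subject with one can enter as soon as it is adjudicated. An event-free subject treated on the same day must wait for a visit no earlier than day 23 (30 ± 7 days). If treated subjects are still waiting at the cut, the set holds their events but not the event-free subjects treated alongside them. The tipping-point analysis does not repair this, because pending subjects have not terminated early. At stake are safety power and an unbiased event rate; the effectiveness endpoint is not affected.

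**Working it through.** **Inputs from the documents.** Performance goal 16.2%; one-sided exact binomial test at 0.05; success if the exact upper 95% bound is below 0.162 (protocol 6.1.1, SAP 5.1.2); 140 for analysis; 156 enrolled; 30-day visit at 30 ± 7 days. **Not visible:** design event rate, stated power, attrition, accrual, time to adjudication. The plan's own power therefore cannot be reproduced. The pair 140 and 156 fits a 10% allowance (140 / 0.90 = 155.6), but that allowance is an inference.

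**Step 1. The triggers side by side.**

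| Treated subject | Counts under 4.1 / SAP 3 | Counts under 6.5 / SAP 5.6 |
|---|---|---|
| Qualifying event | yes | yes |
| Event-free, 30-day visit done | yes | yes |
| Event-free, lost before that visit | yes | no |
| Event-free, 30-day visit missed, later visit done | not by a 30-day visit | yes |

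Apart from the last row, anyone who counts under 6.5 also counts under 4.1. Because 4.1 says at least 140, meeting 6.5 in practice meets 4.1. The reverse fails: with L event-free losses among the 140, the safety n is 140 − L.

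**Step 2. Exact reference.** Let c(n) be the largest count whose one-sided 95% Clopper-Pearson upper bound is below 16.2%. Power = P(X ≤ c(n)), X ~ Bin(n, p). At n = 140 the bound is 16.02% for 15 events and 16.84% for 16, so c = 15. Rejection at 16.2% is 4.45%.

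**Step 3. Safety n below 140.**

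| n | c | Power at 8% | Power at 9% |
|---|---|---|---|
| 140 | 15 | 90.5% | 80.7% |
| 139 | 15 | 91.0% | 81.5% |
| 138 | 14 | 86.0% | 74.0% |
| 133 (5% lost, assumed) | 14 | 88.8% | 78.4% |
| 126 (10% lost, assumed) | 13 | 86.8% | 75.7% |

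The pattern is not monotone: c moves in steps, and one loss slightly raises power.

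**Step 4. Pending subjects, exact ceiling.** Take 140 resolved subjects plus only the events among k pending ones:

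Power = Σₑ P(E = e) × P(X ≤ c(140 + e) − e), E ~ Bin(k, p), X ~ Bin(140, p).

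| True rate | k = 0 | k = 8 | k = 16 |
|---|---|---|---|
| 5% | 99.8% | 99.7% | 99.5% |
| 8% | 90.5% | 86.5% | 81.6% |
| 9% | 80.7% | 74.2% | 67.0% |
| 16.2% | 4.45% | 2.4% | 1.3% |

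Here k = 16 is 156 − 140, a ceiling because some consented subjects are never treated.

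**Step 5. Pending subjects, simulated.** Assumptions: Poisson insertions at 8 or 16 a month; events uniform on days 0-7, available after a lag (event to adjudication) or at the visit if earlier; event-free subjects available at a visit uniform on days 23-37; cut at the 140th available subject; 50,000 runs per setting. Power at a true 9%, 156 treated, no losses:

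| Lag (days) | 8 a month | 16 a month |
|---|---|---|
| 0 | 76.0% | 70.5% |
| 14 | 78.7% | 76.0% |
| 28 | 80.7% | 79.9% |
| 42 | 80.7% | 80.8% |

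At lag 0, about 7 and 14 subjects are pending and the mean estimated rate is 9.4% and 9.8%.

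With few pending the loss is small. With 142 treated, power is 79%. With 10% of 156 never evaluable (156 × 0.90 = 140.4), fewer than 2 are pending and power is 78.0-78.1%, against 79.2-79.5% for the first evaluable subjects by date in the same runs.

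**Step 6. Level.** Rejection at a true 16.2% in the Step 5 settings runs from 1.8% to 4.6%, never above 5%.

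**The case against.** The strongest reply has four parts.

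- **The triggers are nested.** A reader might infer that the two rules are incompatible and imply rival denominators. Step 1 does not support that. Only protocol 6.5 and SAP 5.6 say when the primary analysis is run, and following them satisfies 4.1. This part of the reply stands: the fault is inconsistent wording.
- **Redaction.** Text is blacked out next to the trigger sentence in protocol 4.1 and SAP 3, between protocol 6.3 and 6.5, and in SAP 5.5. A cohort rule may sit there. This also stands: one can say that no visible text closes the cohort, but not that the plan lacks a rule.
- **Stacked assumptions.** The power loss needs a cut at exactly the 140th available subject, nearly all 156 treated, and fast adjudication. At least 140 permits a later cut, and an event counts only once the clinical events committee has adjudicated it, so zero lag is an extreme. At a true 5% the loss is under half a point even with 16 pending. The size is conditional; the outcome-dependent entry rule is in the visible text.
- **Direction.** A reader might infer that a positive safety result would be unsafe. It would not: the bias raises the observed event rate and lowers the rejection probability under the null. The risk is a missed success and an overstated event rate.

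**Conclusion.** The concern holds in limited form. The visible trigger wording is inconsistent between protocol 4.1 / SAP 3 and protocol 6.5 / SAP 5.6, and on 4.1 alone the safety n could fall below 140. The cost of a few losses is small and irregular.

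The population rule also lets events enter ahead of event-free subjects treated on the same dates. Against 80.7% at a true 9%, the assumed conditions give power of about 70-76% at zero lag and 76-79% at 14 days, with no material loss from 28 days on. About 1 point is lost if few subjects are pending, and the loss is negligible at a true 5%. These sizes rest on assumed accrual, lag, number treated and cut point, none of which the visible documents give.

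Type I error is not inflated, and a positive result stays valid. The point is worth fixing before the data cut because the repair is cheap and removes discretion over a co-primary denominator.

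A separate minor mismatch: SAP 5.1.5.2 states "Subject enrollment is capped at 28 per site (20% of the total number of enrollments", and 28 is 0.20 × 140, whereas 0.20 × 156 = 31.2. It does not bear on timing, but it shows that 140 and 156 are not kept apart.

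**What to change.** Put one rule in protocol 4.1 and 6.5 and SAP 3 and 5.6:

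- The primary safety cohort is every subject with the catheter inserted by a cut fixed without regard to outcome, either a date or the first N by insertion.
- The analysis is run once every cohort member has an adjudicated primary safety event, a visit in or after the 30-day window, or documented withdrawal or loss.
- The figure 140 counts subjects evaluable for safety, after losses.
- If 140 is not reached, all evaluable subjects are analysed with the same exact test, and n is reported with the losses and exclusions.

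If N is used, it should allow for losses: N = 148 gives 148 × 0.95 = 140.6 evaluable at an assumed 5% loss. N should not be set at 156, because 156 counts consents and some subjects leave before insertion. Events in subjects treated after the cut can be listed descriptively.

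If redacted text already fixes the cohort, cite it in protocol 6.5 and SAP 5.6 and align protocol 4.1 and SAP 3 with it.

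**Cost.** Wording in four sections, no added subjects or visits, and some delay. In the simulation (true 9%, lag 0, no losses), closing at the 140th insertion moves the cut by a median of 1 to 4 days, though any event-free loss then leaves fewer than 140. Waiting for all 156, if all were treated, takes about 5 weeks at 16 a month and 9 weeks at 8 a month. That analysis passes with up to 17 events and has 83.5% power at 9%.
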